4.2 Control of Systematic Error/Bias

This is a real-world study. Selection of patients will be made from the Investigational site's routine patients. All patients meeting the key eligibility criteria and having signed the ICF will be eligible for enrollment in the study. Control and reduction of potential bias associated with a single-arm study design have been taken into account by defining key inclusion and exclusion criteria to represent a population similar to the patients with AF ablation in the real world and defining a mITT group with population similar to the subjects enrolled in ongoing ADVENT trial and other trials about AF ablation.

4.3 Number of Subjects per Investigative Site

Thirty ATTEMPT or TREATMENT subjects will be enrolled from one site.

5 ADDITIONAL DATA ANALYSES

The additional endpoints will be analyzed after all TREATMENT subjects finishing Twelve-month Visit data collection. The additional endpoints will be analyzed for TREATMENT subjects in ITT set. Descriptive statistics will be conducted for the effectiveness endpoint events. The number, incidence (amount of events/number of subjects) and its 95% confidence interval will be calculated (exact methods).

5.1 Other Endpoints/Measurements

1. AF symptoms assessment: Descriptive analysis of atrial fibrillation symptoms at baseline versus 12 months after the procedure
2. Procedural parameters:
 - Total procedure time (initiation of interventional venous access puncture to all devices remove from the body)
 - Left atrial dwell time (total time an ablation catheter is in the left atrium)
 - Total ablation time (first ablation to last ablation for PVI)
 - Fluoroscopy time (total duration of exposure)

5.2 Interim Analyses

There is no formal statistical hypothesis test in this study, thus interim analysis can be made according to actual needs.

5.3 Subgroup Analyses

The primary and secondary endpoints will be sub analyzed based on the following variables, including but not limited to:

- Gender
- Whether ablation is performed as first-line therapy.
- Whether the subject is enrolled prospectively.

5.4 Univariable Analyses

Univariable analysis will be performed to assess the impact of potential baseline data and clinical characteristics on the primary endpoints.

5.5 Changes to Planned Analyses

Any changes to the planned statistical analyses made prior to performing the analyses will be documented in an amended Statistical Analysis Plan approved prior to performing the analyses. Changes from the planned statistical methods after performing the analyses will be documented in the clinical study report along with a reason for the deviation

6 VALIDATION

All clinical data reports generated per this plan will be validated per 90702587, Global WI: Clinical Data Reporting Validation. The validation level R1 chosen for all primary, secondary, safety and other additional endpoints. The validation program includes checking logs and generating compare reports in comparing with main programming datasets. Statistical analyses and validation will be performed by IQVIA team.

7 PROGRAMMING CONSIDERATIONS

All statistical programming tasks will be performed by IQVIA™ independently.

7.1. Statistical Software

All statistical analyses will be done using The SAS System Version 9.2 software or above (Copyright © 2000 SAS Institute Inc., SAS Campus Drive, Cary, North Carolina 27513, USA. All rights reserved.).

7.2. Format of Output

Statistical analysis will be performed using SAS. All output for the final statistical report will be in the form of a Word document, which may include tables, figures, graphs, and listings, as appropriate.

7.3. Rules and Definitions

For baseline categorical variables, subjects with missing values will not be counted in the corresponding denominators for proportions. Number of patients completing the visit will be considered in denominators.

7.4. The Method of Handling Missing Value and Outliers

The distribution of missing and/or incorrect data will be analyzed separately based on whether the data is collected prospectively or not.

For the missing data, only the missing primary endpoint indicators will be carried forward during analysis, Sensitivity analyses will be performed on the primary safety and effectiveness endpoints to assess the impact of missing data on study results. In addition to worst-case missing data filling, Tipping Point Analysis will be performed as a post-hoc Analysis to assess the impact of different missing data filling methods on the results.

Sensitivity analyses will be performed to assess the impact of unreasonable data on the stability of the results if appropriate.

When calculating rates of all adverse events, both device and/or procedure related with missing event date (i.e. mm/dd/yyyy), the ideal is to work with safety and/or data

management representatives to query sites for missing data. However missing and partial missing dates may be handled as using the worst-case scenario as follows:

Partial Date	Action Taken
Entire adverse event onset date is missing	The procedure date will be used for the onset date.
The month and the day of the month are missing but the year is available	January 1 st will be used for the month and day of the onset date. However, if the imputed date falls before the procedure date, then the procedure date will be used for the onset date.
Day is missing, but the month and year are available	The 1 st will be used as the day of the onset date. However, if the imputed date falls before the procedure date, then the procedure date will be used for the onset date.

Replace_SAP_Final

Final Audit Report

2024-08-07

Created:	2024-08-07
By:	[name] ([contact])
Status:	Signed
Transaction ID:	CBJCHBCAABAATij6lqRz03GBd5EZH4AZhYsBh7_0UPZW
Number of Documents:	1
Document page count:	19
Number of supporting files:	0
Supporting files page count:	0

"Replace_SAP_Final" History

 Document created by [name] ([contact])

2024-08-07 - 7:38:56 AM GMT

 Document emailed to [name] ([contact]) for signature

2024-08-07 - 7:41:18 AM GMT

 Document emailed to [contact] for signature

2024-08-07 - 7:41:18 AM GMT

 Document emailed to [name] ([contact]) for signature

2024-08-07 - 7:41:18 AM GMT

 Email viewed by [contact]

2024-08-07 - 7:45:46 AM GMT

 Email viewed by [name] ([contact])

2024-08-07 - 7:58:42 AM GMT

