11.2.3. The Method of Handling Missing Value and Outliers

Every effort will be undertaken to minimize missing or incorrect data. However, some missingness is inevitable. The reasons for missing or incorrect data will be described in detail and evaluated for assessment of possible bias if appropriate. The distribution of missing and/or

incorrect data will be analyzed too, which will be separately analyzed based on whether the data is collected prospectively or not.

For the missing data, only the missing primary endpoint indicators will be carried forward during analysis, and the specific carry forward method will be explained in SAP. Sensitivity analyses will be performed on the primary safety and effectiveness endpoints to assess the impact of missing data on study results. In addition to worst-case missing data filling, Tipping Point Analysis will be performed as a post-hoc Analysis to assess the impact of different missing data filling methods on the results.

Error and unreasonable data will be checked and confirmed during data cleansing prior to statistical analysis. Error data will be corrected before analysis, and sensitivity analyses will be performed to assess the impact of unreasonable data on the stability of the results if appropriate.

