 - Other uncontrolled medical conditions that may modify device effect or increase risk, including uncontrolled diabetes mellitus (HgbA1c $> 8.0\%$ if test result already obtained), untreated obstructive sleep apnea or active alcohol abuse
8. Clinically significant psychological condition that in the Investigator's opinion would prohibit the subject's ability to meet the protocol requirements.
9. Employees/family members of:
 - Boston Scientific or any of its affiliates or contractors
 - The Investigator, sub-Investigators, or their medical office or practice, or healthcare organizations at which study procedures may be performed

10. Subjects known to require or have accepted ablation outside the PV region during the procedure except CTI region ablation.

**TTE obtained \leq 6 months prior to procedure will be acceptable, unless a cardiac event has occurred (e.g. MI, acute heart failure or acute onset heart failure) between the date of the exam and the procedure. In this case, a new TTE is needed to confirm eligibility for mITT. The most recent report before the procedure will be used. LA anteroposterior diameter measured by M-mode from the parasternal long-axis view will be used.*

#The absence of thrombus must be confirmed by means of a trans-esophageal echocardiogram (TEE) within 48 hours prior to the procedure or Intracardiac Echography (ICE) during the procedure.

⌘ Cardiac CT/MRI obtained \leq 3 months prior to procedure will be acceptable.

Statistical Methods

Primary Statistical Hypothesis: There are no formal hypotheses testing in this small sample size observational study.

Statistical Test Method: Descriptive statistics will be conducted for the endpoint events. Explorative statistical analysis might be produced if appropriate, such as Bayesian estimation of the study results using ADVENT data as the prior.

Primary effectiveness endpoints will be summarized for TREATMENT subjects in modified Intent-to-Treat (mITT) set.

Secondary effectiveness endpoints will be summarized for TREATMENT subjects in Intent-to-Treat (ITT) set and mITT set respectively.

Primary and secondary safety endpoints will be summarized for ATTEMPT and TREATMENT subjects in ITT set.

The additional endpoints will be summarized for TREATMENT subjects in ITT set.

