3 ENDPOINT ANALYSIS

3.1 Primary Effectiveness Endpoint:

The primary effectiveness endpoint is acute Procedural Success, defined as proportion of subjects that achieve electrical isolation of all PVs using FARAPULSE Pulsed Field Ablation system only.

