3.2.1 Hypotheses

This is an observational real-world study with small sample size, no formal hypothesis is performed in this study.

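### Carry-forward is the main rule for missing primary endpoint values, but it has no stated method and does not suit a one-time acute result or a 7-day event composite

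*SAP*

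**What the plan says.** SAP 7.4 gives the main rule: "only the missing primary endpoint indicators will be carried forward during analysis". Protocol 11.2.3 has the same rule and adds that "the specific carry forward method will be explained in SAP". The SAP drops that clause. It names no source value, time point or denominator for the filled data.

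Both sections add sensitivity analyses: "In addition to worst-case missing data filling, Tipping Point Analysis will be performed as a post-hoc Analysis". SAP 7.4 also has a table for adverse events with missing onset dates; an event with no date at all is placed on the procedure date.

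SAP 7.3 has a rule for missing baseline categorical values, followed by a sentence with no stated scope: "Number of patients completing the visit will be considered in denominators".

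The endpoints concerned are acute procedural success, settled at the index procedure, and a composite of serious related events at 7 days. On testing, SAP 3.2.1 states that "no formal hypothesis is performed in this study". Neither document sets a margin or a performance goal.

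**The concern.** Carrying a value forward needs an earlier measurement of the same quantity that is a fair stand-in for the missing one. Neither primary endpoint offers that.

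- **Acute success.** The procedure data list in Protocol 10.5.2 names one isolation result per vein and no interim results. If an earlier check were found in the records, it would come before the waiting period that exists to reveal reconnection.
- **Safety.** The last known status of a subject with no recorded event is event-free. Carrying that forward turns an unknown into a favourable outcome.

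Both errors flatter the device. With about 30 subjects, each unknown outcome is worth 1/30 = 3.3 percentage points. Protocol 4.2 and 7.3 say the data are meant to support registration in China. Protocol 11.2.3 accepts that some data will be missing, and retrospective subjects are followed on the site's own schedule.

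**Working it through.** **Inputs.** n = 30 (SAP 4.3); two-sided 95% exact intervals (SAP 3.1.3 and 3.2.3); no missing-data rate in either document. I assume 1 to 3 missing values.

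**Formula.** Clopper-Pearson for x events in n: lower limit = Beta(0.025; x, n-x+1), upper limit = Beta(0.975; x+1, n-x), as quantiles. For x = 0 the upper limit is 1 - 0.025^(1/n). For x = n the lower limit is 0.025^(1/n).

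**The plan's own table first.** For 0/30: 1 - 0.025^(1/30) = 11.57%, stated as 11.6%. For 1, 2 and 3 events: 0.08-17.22%, 0.82-22.07% and 2.11-26.53%. All four rows of SAP 3.2.2 reproduce.

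**Safety, no observed events, m outcomes unknown:**

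| m | Carried forward as no event | Known outcomes only | Worst case |
|---|---|---|---|
| 1 | 0/30, upper 11.6% | 0/29, upper 11.9% | 1/30 = 3.3% (0.1-17.2%) |
| 2 | 0/30, upper 11.6% | 0/28, upper 12.3% | 2/30 = 6.7% (0.8-22.1%) |
| 3 | 0/30, upper 11.6% | 0/27, upper 12.8% | 3/30 = 10.0% (2.1-26.5%) |

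The first column does not change with m: under carry-forward, missing data cost nothing in the reported rate or its precision.

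**Acute success, all documented results successes, m results undocumented:**

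| mITT size | m | Filled as success | Counted as failure |
|---|---|---|---|
| 30 | 1 | 100% (88.4-100%) | 29/30 = 96.7% (82.8-99.9%) |
| 30 | 2 | 100% (88.4-100%) | 28/30 = 93.3% (77.9-99.2%) |
| 30 | 3 | 100% (88.4-100%) | 27/30 = 90.0% (73.5-97.9%) |
| 20 | 3 | 100% (83.2-100%) | 17/20 = 85.0% (62.1-96.8%) |

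The documents give no expected mITT size, so 30 is the largest case for 30 enrolled subjects and 20 is an assumed smaller one.

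**Tipping point.** The method finds the number of adverse imputations at which a conclusion reverses. With no hypothesis, margin or goal, no conclusion is defined, so there is no such number. Calling the analysis post-hoc while writing it into the plan adds to the confusion.

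**Windows.** Protocol Table 6.2-1 counts phrenic nerve palsy according to its status at the 1-month visit. It lets pericarditis and gastric motility disorders qualify by lasting more than 30 days. Knowing a subject's status at day 7 therefore does not settle every component.

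**The case against.** Several stronger readings are tempting, and the documents do not support them.

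- *Carry-forward is impossible for acute success.* Protocol 5.3.2 and 10.5.1.2 describe periodic checks before the final one, so an earlier result could exist and be carried. It would be optimistic and is not on the data list, but the rule is not impossible.
- *Every unknown safety outcome becomes no event.* The SAP does not say so. A palsy seen at the end of the procedure, with no 1-month check, would carry forward as unresolved and count as an event. The missing-date table also works against the device, but only for events already reported; it says nothing about subjects whose event status is unknown.
- *A missed 7-day contact means an unknown outcome.* The primary analysis waits for the 1-month data. That contact collects adverse events and admissions (Protocol 10.7), and all adverse events are reportable (Protocol 18.1). Day-7 status can often be recovered, so the number truly unknown may be small.
- *SAP 7.3 removes subjects, even deaths, from the endpoint denominators.* Its sentence follows one limited to baseline variables, and SAP 4.1 sets the endpoint populations separately. Ambiguity is all that can be claimed.

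The strongest objection is about size. Worst-case filling is already planned, so the 6.7% and 10.0% figures would be reported anyway. Moving the main safety estimate from carry-forward to known outcomes, with 2 unknown, keeps it at 0% and raises the upper limit by 12.3 - 11.6 = 0.7 points. That stands for safety. It does not answer the acute success figures, where the main estimate itself moves. Nor does it excuse a main rule whose method the protocol promised and the SAP omits: two analysts could follow it and report different rates.

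**Conclusion.** The point holds. Carry-forward is the stated main rule for both primary endpoints, its method is undefined, and its natural application favours the device. The effect on the main safety estimate is small: 0/30 against 0/28 with 2 unknown. For acute success it is larger: 100% against 90.0% with 3 undocumented results of 30. The planned worst-case analysis limits the harm without changing the main estimate, and the tipping-point analysis adds nothing as specified.

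The direction of bias assumes that the last recorded status is what gets carried, which the SAP does not state. The figures assume the missing counts shown, no observed safety events, and success in every documented isolation result. If nothing is missing, nothing changes.

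**What to change.** Amend SAP 7.4 and Protocol 11.2.3 as follows.

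1. Delete carry-forward.
2. **Acute success:** count a vein without documented isolation as not isolated. This is stricter than the safety rule because the result belongs to the procedure record and has no later source.
3. **Safety:** include all ATTEMPT and TREATMENT subjects who had a primary safety event, or whose status is known for the full window each component needs. That is day 7, plus the 1-month or 30-day status that Table 6.2-1 uses for phrenic nerve palsy, pericarditis and gastric motility disorders. Use the 1-month contact to establish status. Its window is days 23 to 37 (30 ± 7), so a condition still present at a contact up to day 30 also needs its resolution date. List the subjects with unknown status and count them as events in the worst-case analysis.
4. State that the visit-completer denominator in SAP 7.3 does not apply to the primary endpoints.
5. Replace the tipping-point analysis with best-case and worst-case bounds.

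Cost: an amended SAP and a protocol amendment, which needs ethics committee approval (Protocol 13 and 15.3). The rates may look slightly less favourable, mainly where records of isolation are thin. If the analyses have already been run, SAP 5.5 requires the change and its reason to be given in the clinical study report.
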